## **10.1 EVALUATION DURING TREATMENT/INTERVENTION**

No additional tests or follow-up over the standard intra-operative and post-operative monitoring will be required in this trial.

The tests included under standard of care are:

- CBC
- Coagulation tests
- Pre-operative technetium lymphoscintigraphy (TcL)

## 11.0 TOXICITIES/SIDE EFFECTS

COMMON, SOME MAY BE SERIOUS  In 100 people receiving ICG dye, more than 20 and up to 100 may have:  • Mild burning at the injection site lasting up to a few hours • Green or yellowish discoloration at the injection site lasting up to several hours
OCCASIONAL, SOME MAY BE SERIOUS  In 100 people receiving ICG dye from 4 to 20 may have:  • General yellowish skin discoloration lasting up to 24 hours • Orange urine discoloration lasting up to 24 hours
RARE, AND SERIOUS  In 100 people receiving ICG dye 3 or fewer may have:  • Allergic reaction – most are mild with pruritus and hives, but some can be serious with wheezing/bronchospasm and facial edema

## 12.0 CRITERIA FOR THERAPEUTIC RESPONSE/OUTCOME ASSESSMENT

Please refer to sections 4.0 and 9.0 for the overview of the study design, intervention, and treatment plan.

## 13.0 CRITERIA FOR REMOVAL FROM STUDY

- Patient refuses to continue with study
- Immediate adverse reaction to ICG injection precluding complete dosing

## 14.0 BIOSTATISTICS

**Primary objective**

Non-inferiority studies concentrate on proving that the tested method is not clinically inferior to the standard of care by a particular margin decided upon using prior knowledge of the external (to the trial) advantages of the new method. They are extremely useful in rare conditions and when comparing a new test to a standard of care with a very high success rate. Both TcL and ICG have a success rate of 95% and pediatric solid tumors requiring SLN biopsy are rare. In order to perform a standard superiority study comparing ICG to TcL, thousands of patients would be necessary, which is not clinically feasible. As described above, from the clinical standpoint, ICG is superior to TcL for patient care because it provides much more accurate visualization of SLNs during biopsy, does not expose the patient to radiation, does not require painful injections without sedation, and does not require additional time commitments from the patient and family. The non-inferiority margin was, therefore, set at 10% using this clinical knowledge. Using an alpha level of 0.05 and a beta level of 0.2, and knowing TcL and ICG detect a SLN in 95% of cases, the calculated N per group for paired values is 59. Because each patient serves as his/her own control, these tests are considered “paired” values. Adjustment to the non-inferiority study statistics has been described by Liu et al (7). Given that each of our patients will be evaluated with both TcL and ICG, each case counts towards both groups and our total N = 59. Given the rate of 15-20 pediatric SLN biopsies per year at our institution, patient accrual should be completed within approximately 4 years.

The primary outcome of this study is the detection rate (% of patients in whom a SLN is identified) for ICG and TcL. These percentages will be compared using a non-inferiority comparison for matched pair data as described above. In the unlikely event that SLNs are not found with either modality, these patients will still contribute data to the primary endpoint (i.e. decreasing the detection rate for both modalities) and safety data, but will not contribute to the other secondary aims.

### **Secondary objectives**

Safety will be analyzed with descriptive statistics of the number and type of adverse reactions encountered (per CTCAE guidelines).

The number of nodes identified by each technique will be compared using a paired Wilcoxon signed-rank test.

To evaluate sensitivity, the percent of patients in whom a SLN is found to contain tumor on pathology using each technique will be compared with McNemar's test for matched pair data.

Finally, to determine whether the intensity of each node is associated with pathologic positivity, a logistic regression model will be fit with pathologic positivity as the outcome and intensity as the predictor, and robust standard errors will account for correlation among multiple nodes per patient. This will be done separately for ICG and TcL intensity.

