## **1.0 PROTOCOL SUMMARY AND/OR SCHEMA**

This prospective trial will examine whether indocyanine green (ICG)-guided intraoperative transdermal lymphography is non-inferior to pre-operative technetium lymphoscintigraphy (TcL) for detecting sentinel lymph nodes (SLN) in pediatric patients with solid tumors. The primary endpoint is the detection rate for TcL-labeled and ICG-labeled SLNs. Secondary outcomes will include safety of ICG, number of positive nodes detected with each modality in each patient, and the sensitivity rate with each modality. The study population will include any patient under the age of 30 years who requires a sentinel lymph node biopsy for a solid tumor. Each patient will undergo both TcL prior to SLN biopsy and intra-operative ICG transdermal lymphography, thereby simultaneously serving as his/her own control. However, the surgeon will be blinded to the TcL results until after the ICG transdermal lymphography results have been recorded, in order to directly evaluate the detection rate of the ICG. Given the estimated sample size of 59 patients and an annual rate of SLN biopsies on patient under 30 years of age of 10 per year at MSK and 17 patients from the two collaborating institutions, this study will take approximately 4 years to complete. (Schematic provided below)

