## 2.1 OBJECTIVES AND SCIENTIFIC AIMS

- Primary Objective
  - Show that the SLN detection rate using ICG-guided transdermal lymphography is not inferior to that of TcL in pediatric solid tumors
- Secondary Objectives
  - Safety of ICG injection
  - Compare the total number of ICG+ and TcL+ SLNs harvested in each patient
  - Compare the percent of patients who have a pathologically positive SLN identified with each technique (sensitivity rate)

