## 3.0 BACKGROUND AND RATIONALE

Pediatric solid tumors vary greatly in their propensity to spread to regional nodes. After the development of SLN biopsy in melanoma and breast cancer in adults, pediatric surgeons adopted the technique and applied it to multiple tumors including melanoma, Spitz nevi, and soft tissue sarcomas. Technetium lymphoscintigraphy is the gold standard for mapping and identifying SLNs in pediatric patients with solid tumors. Some surgeons also inject blue dye at the site, but its use has decreased because of frequent hypersensitivity reactions (1,2).

The standard procedure for SLN biopsy includes TcL the morning of or day prior to surgery. Mapping of the SLN is accomplished with nuclear medicine scans shortly after local Tc injection; the scans identify which lymph node basin contains the SLN and how many SLNs there are (average 1-2). In the unlikely event (<3%) that mapping fails, the patient is brought back 2-3 weeks later for repeat mapping. Once mapping is confirmed, the patient is taken to the OR, where a gamma probe is used to identify the hottest point (point with the highest gamma count) on the skin overlying the lymph node basin and an incision is made. The gamma probe and blunt dissection are then used to find the hot node and it is then resected. Given the lack of specificity and resolution using the gamma probe this can result in significant time and dissection. All the hot (gamma probe positive) nodes are removed and the procedure is considered complete when the baseline gamma count of the basin is <10% of the gamma count of the hottest node.

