## 4.1 OVERVIEW OF STUDY DESIGN/INTERVENTION

### 4.2 Design

This is a prospective, multi-institutional clinical trial to evaluate non-inferiority of ICG-guided SLN biopsy compared with the gold standard TcL-guided SLN biopsy in pediatric patients with solid tumors. Each patient will undergo TcL, consistent with the standard of care, but the surgeon will be blinded to the results preoperatively. Intraoperatively, ICG injection and transdermal lymphography will be used to identify the draining nodal basin and the position of the sentinel nodes. ICG transdermal lymphography will be considered successful if SLNs can be visualized on near-infrared imaging. After the transdermal lymphography results have been recorded, the surgeon will be unblinded to the TcL mapping. All ICG-positive and TcL-positive nodes will be removed and complete excision will be confirmed by intra-operative near-infrared imaging and gamma probe evaluation. Thus, in this trial each patient will serve as his/her own control. If TcL fails, no repeat TcL will be performed, the SLN biopsy will be done with ICG alone, and the patient will be recorded as a failure of TcL (i.e. decreasing the detection rate for TcL). If ICG mapping fails, the TcL results will be used to perform SLN biopsy and the patient will be considered a failure of ICG (i.e. decreasing the detection rate for ICG). In the <1% of patients that fail both TcL and ICG, no SLN biopsy will be performed and the patient will be recorded as a failure of both TcL and ICG. These patients will still contribute data to the primary endpoint (i.e. decreasing the detection rate for both modalities) and safety data, but will not contribute to the other secondary aims. Approximately 59 patients will be enrolled over a period of approximately 4 years.

The primary outcome, SLN detection rate, will be compared between ICG-guided transdermal lymphography and TcL to determine non-inferiority of ICG in this clinical application. Secondary outcomes include the safety of ICG in this clinical scenario, comparisons of the total number of excised nodes identified with each detection method in each patients, and the sensitivity rate (percent of patients with a pathologically positive SLN) for each technique.

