### 4.3 Intervention

On the day of or the day before the scheduled OR procedure, the patient will undergo TcL, but the surgeon will be blinded to the results preoperatively. On the day of surgery, 4 cc of 1.25 mg/mL ICG will be injected at 4 points directly surrounding the tumor site (1cc per point, depth will vary with position of the tumor) after the patient is under anesthesia. Transdermal lymphography and analysis of all possible draining nodal basins will then be performed using a near-infrared camera in real time. ICG mapping to the SLN takes approximately 5min. If the SLN cannot be identified 20min after ICG injection, it will be considered a failure of ICG, and the TcL results will be used to perform the SLN biopsy. If the ICG does map and a SLN is identified, the transdermal lymphography results will be recorded and the surgeon will be unblinded to the TcL results. All fluorescent lymph nodes will then be resected using the near-infrared camera. After all ICG-positive nodes have been resected, but before closure, gamma probes will be used intraoperatively to ensure all TcL-positive SLNs have been removed. As is standard with TcL SLN biopsy any activity in the nodal bed <10% of the “hottest” node removed will be considered background. This will act as the threshold for all TcL positive nodes being removed. The detection rates for each tracer, ICG and TcL positivity for every node removed, and number of ICG and TcL positive nodes per patient will be recorded. If TcL fails, no repeat TcL will be performed, the SLN biopsy will be done with ICG alone, and the patient will be recorded as a failure of TcL (i.e. decreasing the detection rate for TcL). If ICG mapping fails, the TcL results will be used to perform SLN biopsy and the patient will be considered a failure of ICG (i.e. decreasing the detection rate for ICG). In the <1% of patients that fail both TcL and ICG, no SLN biopsy will be performed and the patient will be recorded as a failure of both TcL and ICG with respect to detection rate. These patients will still contribute data to the primary endpoint (i.e. decreasing the detection rate for both modalities) and safety data, but will not contribute to the other secondary aims.

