### **16.1 DATA MANAGEMENT ISSUES**

All experimental data including TcL, ICG mapping and detection, nodal ICG and TcL measurements and correlating pathology results will be stored in a REDCap database. Data from patients accrued at other institutions will also be submitted to the secure REDCap

database. External institutions will only have access to patient information submitted from their respective institution. The PI and MSK research team will be the only researchers with access to other institutions data submissions.

Data will be managed through REDCap (Research Electronic Data Capture), a data management software system supported by Clinical Research Administration at MSK. Members of the Clinical Research Administration supporting the REDCap software will have access to the data for the purpose of ensuring the proper functioning of the database and the overall software system. REDCap is a tool for the creation of customized, secure data management systems including web-based data entry forms, reporting tools, and a full array of security features including user and group based privileges with a full audit trail of data manipulation and export procedures. REDCap is maintained on MSK-owned servers that are kept in a locked server room with appropriate environmental modifications (e.g., special air conditioning), supported by an uninterrupted power supply, and backed up nightly with some backup tapes stored off-site. All connections to REDCap utilize encrypted (SSL-based) connections. Nationally, the REDCap software is developed, enhanced, and supported through a multi-institutional consortium led by the Vanderbilt University CTSA. REDCap will only be used for the housing of survey data. Use of REDCap has been approved by the department's manager of IT Systems and by MSK Information Security.

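### The secondary 'sensitivity rate' is defined over all analysed patients rather than node-positive ones, so it measures node positivity and would understate both tracers' sensitivity and any gap between them

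*Combined protocol and SAP*

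**What the plan says.** The measure appears in four places in the combined protocol and SAP.

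- **Section 14.0, Secondary objectives.** To evaluate sensitivity, the plan takes "the percent of patients in whom a SLN is found to contain tumor on pathology using each technique" and compares the two percentages with McNemar's test.
- **Section 4.2, Design.** The secondary outcome is the "sensitivity rate (percent of patients with a pathologically positive SLN) for each technique".
- **Section 2.1, Objectives.** The aim is worded "Compare the percent of patients who have a pathologically positive SLN identified with each technique (sensitivity rate". This can be read with either denominator: all patients, or only those who have a positive node.
- **Section 1.0, Summary.** It lists "the sensitivity rate with each modality" and gives no definition.

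The one stated restriction on who is analysed concerns patients in whom both modalities fail. Section 14.0 (Primary objective) says that they count for the primary endpoint and for safety but "will not contribute to the other secondary aims". Section 4.2 expects fewer than 1% of patients to be in this group.

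**The concern.** Sensitivity is conditional on disease: among patients with tumour in a sentinel node, it is the share whom the technique identifies. The two explicit definitions, in Sections 4.2 and 14.0, use all analysed patients instead. A node-negative patient, in whom there is nothing to find, then counts against both tracers.

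Two consequences follow. The reported level depends on how many patients have nodal disease, and Section 3.0 itself says "Pediatric solid tumors vary greatly in their propensity to spread to regional nodes". The figure would therefore move with the tumour mix even if the tracers performed identically throughout. The absolute gap between tracers also shrinks in proportion to the node-positive share, so a small reported gap could hide a large loss.

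This is the only planned patient-level comparison of whether each tracer finds the tumour-bearing node. The primary endpoint asks only whether any SLN is identified. Section 3.0 envisages dropping TcL if ICG proves non-inferior, so a diluted gap presented under the name of sensitivity could give false reassurance.

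**Working it through.** **Inputs from the documents.** Total N = 59 (Section 14.0). Double failures are under 1% (Section 4.2), so about 58 to 59 patients are analysed. No node-positive proportion is given.

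**The plan's own figure.** The documents give no number for the sensitivity endpoint; the only figure to reproduce is N. With 95% detection for both tracers, a 10% margin, one-sided alpha 0.05 and 80% power:

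N = 2 × 0.95 × 0.05 × (1.645 + 0.842)² / 0.10² = 0.095 × 6.18 / 0.01 = 58.7, rounded up to 59.

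This matches. The plan does not state sidedness; one-sided 0.025 would give 75.

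**What the defined quantity measures.** Let D be the number of node-positive patients, X the number of them found by a technique, and N the number analysed.

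- As written: X / N = (D / N) × (X / D), which is proportion node-positive × sensitivity.
- Sensitivity: X / D.
- The gap as written is therefore (D / N) × the difference in sensitivities.

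**Size.** Assume 10%, 20% or 30% node-positive. Rounded to whole patients, D = 6, 12 or 18 of 59. For illustration, also assume that TcL misses none of them and ICG misses three. D is counted here as patients positive by either tracer.

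| Node-positive (D) | TcL as written | ICG as written | Gap as written | ICG over D (exact 95% CI) | Paired difference over D, points (95% CI) |
|---|---|---|---|---|---|
| 6 | 6/59 = 10.2% | 3/59 = 5.1% | 5.1 | 3/6 = 50% (12 to 88) | 50 (-9 to 81) |
| 12 | 12/59 = 20.3% | 9/59 = 15.3% | 5.1 | 9/12 = 75% (43 to 95) | 25 (-5 to 53) |
| 18 | 18/59 = 30.5% | 15/59 = 25.4% | 5.1 | 15/18 = 83% (59 to 96) | 17 (-4 to 39) |

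The exact limits are Clopper-Pearson and the paired limits are Tango score intervals. For three discordant patients against none among 59, the Tango interval around 5.1 points is -1.3 to 13.9 in all three rows. TcL is 100% over D throughout, yet would be reported as 10.2% to 30.5%.

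**Effect of tumour mix.** Hold the loss of sensitivity fixed at 25 points. The gap as written would be 25 × 6/59 = 2.5, 25 × 12/59 = 5.1 or 25 × 18/59 = 7.6 points, depending only on the node-positive share.

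**Excluding a double failure.** With one removed, 12/58 = 20.7% and 9/58 = 15.5%. The exclusion does not cure the problem.

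**The test.** McNemar's test uses only the discordant patients. With three against none, the exact two-sided p-value is 2 × 0.5³ = 0.25 under either denominator.

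**The case against.** The strongest reply is that the planned inference does not change. McNemar's test is the only analysis specified for this endpoint, and its p-value is the same with either denominator. That is correct, and it confines the fault to the percentages, their difference and their name. The primary endpoint, N and the margin are untouched.

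Second, because each patient receives both tracers, the denominator cancels in a ratio: 9/59 over 12/59 is 75%. The ratio of the two sensitivities can therefore be recovered, and tumour mix cannot create a difference where none exists. This also stands. But the plan reports percentages, not a ratio, and the absolute levels and gap are still scaled down by the node-positive share. A ratio would also not give either tracer's own sensitivity unless the other missed nothing.

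Third, Section 2.1 can be read as the share of node-positive patients identified, so Sections 4.2 and 14.0 might be loose shorthand for that. The reading is possible, but an ambiguous objective does not override two explicit definitions, one of them in the analysis section.

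Fourth, other analyses touch on tumour-bearing nodes. Section 14.0 also models pathologic positivity on node intensity, but separately for each tracer, so it does not compare detection between them. The node counts, as Section 2.1 shows, are of tracer-positive nodes.

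Last, only tracer-positive nodes are planned for removal, so no true sensitivity can be estimated and the intervals will be wide. Both points are right. They call for the label relative sensitivity and for showing the intervals. The numerator also needs care: the plan does not say how a node found by gamma probe after unblinding counts if it then fluoresces.

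**Conclusion.** The concern holds. Sections 4.2 and 14.0 define an SLN positivity rate and call it sensitivity. This does not depend on any assumed prevalence: whenever some analysed patients are node-negative, a tracer that misses nothing scores below 100%.

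The size does rest on assumptions. The 10% to 30% node-positive range and the three ICG misses against none are illustrations, not figures from the documents. On that basis, perfect performance is reported as 10.2% to 30.5%, and one reported gap of 5.1 points stands for a loss of anywhere from 17 to 50 points.

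The error should be corrected before analysis. It is confined to the estimates and labels of a secondary endpoint and leaves the McNemar result and the primary comparison intact.

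**What to change.** 1. In Sections 2.1, 4.2 and 14.0, rename the current measure SLN positivity rate, and align the label in Section 1.0. It can still be reported.
2. Define relative sensitivity for each tracer as patients with a pathologically positive SLN identified by that tracer, divided by patients with at least one pathologically positive SLN removed by either tracer. State that disease missed by both tracers is unseen.
3. State that a patient in whom only one tracer fails to map stays in the denominator if node-positive and counts as not detected by that tracer. State also which reading decides a node's tracer status when it is found only after unblinding.
4. Report each tracer with an exact 95% confidence interval and the paired difference with an interval for paired proportions, such as Tango's score interval. McNemar's test may stay.

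No new data are needed. Section 4.3 already records "ICG and TcL positivity for every node removed", and under Section 16.1 "nodal ICG and TcL measurements and correlating pathology results will be stored in a REDCap database". The cost is an amendment to wording. The drawback is a small denominator with wide intervals, such as 43% to 95% for 9 of 12. Even a perfect 6 of 6 has a lower exact limit of only 54%. That uncertainty is already in the data; the present definition conceals it.

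### The two node-intensity models name no small-sample form for the robust standard error; if tumor-positive nodes are few, the usual uncorrected form rejects a true null too often

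*Combined protocol and SAP*

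**What the plan says.** The last paragraph under Secondary objectives (section 14.0) states that "a logistic regression model will be fit with pathologic positivity as the outcome and intensity as the predictor". It adds that "robust standard errors will account for correlation among multiple nodes per patient" and that "This will be done separately for ICG and TcL intensity". So there are two node-level models with one predictor each, clustered on patient. The paragraph does not say which robust variance will be used, whether the test refers to a normal or a t distribution, what significance level applies, or what happens if very few nodes contain tumor.

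The size of the data set has to be pieced together. Under Primary objective, "the calculated N per group for paired values is 59", based on "knowing TcL and ICG detect a SLN in 95% of cases". Section 3.0 says that mapping scans show "how many SLNs there are (average 1-2" per patient. No section gives an expected share or number of tumor-positive nodes.

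The intensity analysis is not among the objectives in section 2.1, nor among the secondary outcomes in sections 1.0 and 4.2.

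**The concern.** A clustered sandwich variance is justified for large numbers of clusters. It is built from squared fitted residuals, which are on average smaller than the true errors, most of all in the high-leverage clusters that dominate a sparse logistic fit. With fewer than 60 patients, and most of the information carried by the few who have a positive node, the standard error tends to be too small. Intervals for the odds ratio are then too narrow, and the test rejects more often than its nominal level.

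At stake is whether a chance association between brightness or gamma count and tumor is reported as a finding. The question is put inferentially, twice, on a small data set, and the wording leaves the analyst free to use the version that behaves worst there.

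**Working it through.** **The plan's own figure.** The only figure given is the sample size. With 95% detection for both methods, a 10% margin and 80% power, n = (z_alpha + z_beta)² × [0.95×0.05 + 0.95×0.05] / 0.10². One-sided alpha 0.05 gives (1.645 + 0.842)² × 9.5 = 58.7, so 59, which matches. One-sided 0.025 gives (1.960 + 0.842)² × 9.5 = 74.6, so 75. The 0.05 in section 14.0 is therefore a one-sided level for the primary endpoint. It does not set a level for the intensity models, and a two-sided 5% test is assumed below.

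**Size of each model.** Patients contributing nodes: 59 × 0.95 ≈ 56 (59 at most). Nodes: 56 × 1 to 56 × 2 = 56 to 112; at a mean of 1.5, 84. Positive nodes at assumed shares of 10%, 15%, 20% and 30% of 84: about 8, 13, 17 and 25.

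**Variance forms.** With A = X'WX, residuals r_g in patient g, and G patients:
- Uncorrected: A⁻¹ (Σ X_g' r_g r_g' X_g) A⁻¹, normal reference.
- Simple factor: the same times G/(G−1), t on G−1 degrees of freedom.
- Mancl-DeRouen: r_g replaced by (I − H_gg)⁻¹ r_g, where H_gg is the patient's leverage block, t on G−2 degrees of freedom.

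**Null simulation 1.** 56 patients; one or two nodes each (mean 1.5) or one to four; normal or log-normal intensity; within-patient correlations 0 to 0.5; 6,000 replicates per setting. Share rejected:

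| Positive share (assumed) | Positive nodes | Uncorrected, z | G/(G−1), t |
|---|---|---|---|
| 5% | 4-6 | 11-17% | 10-16% |
| 10% | 8-12 | 7.4-9.8% | 6.8-8.8% |
| 15% | 13-18 | 6.1-8.2% | 5.3-7.3% |
| 20% | 17-24 | 5.3-7.4% | 4.8-6.5% |
| 30% | 25-36 | 5.3-7.1% | 4.6-6.1% |

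Central case (one or two nodes, correlations 0.3, normal intensity, 20,000 replicates): 9.2%, 7.1%, 6.2% and 5.6% at 10%, 15%, 20% and 25% positive. The median robust standard error is 0.795, 0.875, 0.916 and 0.928 of the true standard deviation of the estimate. With 200 patients and 20% positive the rate falls to 5.4%, which marks this as a small-sample effect.

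**Null simulation 2.** A different data model: patient random intercept, mean 1.55 nodes, log or raw log-normal intensity. It was run with 59 patients (intercept SD 1.0-2.5, 4,000 replicates) and with 56 patients (SD 1.5). Combined ranges:

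| Positive nodes | Uncorrected, z | Mancl-DeRouen, t |
|---|---|---|
| about 7 (SD 1.5 only) | 11.8% | 7.6% |
| about 9 | 8.0-10.0% | 4.7-6.5% |
| 13-14 | 6.8-8.4% | 3.5-5.2% |
| 17-18 | 5.8-7.1% | 3.5-4.5% |
| 26 (56 patients only) | 5.8-6.5% | 3.2-4.4% |

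The simple factor with t still rejects 7.1-9.1% at about 9 positives.

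**Why the simple factor falls short.** At G = 56 it multiplies the standard error by √(56/55) = 1.009, and the t critical value is 2.004 against 1.960. Together they widen the interval by 1.009 × 2.004/1.960 = 1.032, about 3%. At 10% positive the median standard error is short by 1 − 0.795 = 20%.

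Monte Carlo error is about 0.3-0.5 points per setting, and 0.2 in the 20,000-replicate runs. Simulation 1 leaves out data sets with separation or fewer than two positive nodes; in several of the settings with one to four nodes and 5% positive this was 2-4% of data sets. CR2 was not simulated.

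**The case against.** The strongest reply is that the size of the effect rests on a number the documents do not contain. Eligibility covers any extracoelomic solid tumor needing sentinel node biopsy under age 30, and section 3.0 itself says such tumors differ widely in nodal spread. If 20-30% of nodes are positive, even the uncorrected test rejects only about 5-7% of true nulls. This stands: any figure must be tied to an assumed event count.

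Second, a reader might infer that the plan has chosen the uncorrected form. The text does not say so; a bias-corrected clustered variance fits the same sentence. What is wrong is that the form is left open, and that even the common simple correction leaves 7-9% at about 9 positives.

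Third, a reader might infer that a false association would influence which nodes surgeons leave behind. Nothing supports this. Sections 4.2 and 4.3 have all ICG-positive and TcL-positive nodes removed, and no section uses the intensity models to select nodes.

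Fourth, the correction is not perfectly calibrated: 7.6% at about 7 positives and below 5% at 17 or more. Penalized likelihood or a patient-level permutation test might also serve; neither was compared. This stands as well. It is a reason to add a sparse-event rule, not a reason to leave the variance unnamed.

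**Conclusion.** The gap is real and minor. If the uncorrected sandwich with a normal reference is used, a nominal two-sided 5% test of no association rejects in about 7-10% of cases at about 9 positive nodes (roughly 10% of nodes), 6-8% at 13-14 and 5-7% at 17-26. At about 5 or fewer it rejects in more than 10%; one setting passes 10% already at about 7. The simple G/(G−1) factor with t removes most of the excess only from about 20% positive upward.

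These figures assume 56-59 contributing patients, one or two nodes each on average (somewhat more in the settings with one to four), a two-sided 5% level, and assumed positivity shares, intensity distributions and within-patient correlations. They do not show that this trial's error rate will be any particular value. The primary endpoint, the sample size of 59 and the objectives in section 2.1 are unaffected.

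**What to change.** In the last paragraph of Secondary objectives, replace the general reference to robust standard errors with three statements:

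- The variance is a bias-corrected cluster-robust estimator, clustered on patient (Mancl-DeRouen, which was checked here, or CR2).
- Tests and intervals use a t reference with degrees of freedom equal to the number of patients contributing nodes to that model, minus 2.
- If about 10 or fewer nodes in a model are tumor-positive, the odds ratio and its interval are reported descriptively, without a p-value. The cut-off is a working choice from the simulations: the corrected test rejects 4.7-6.5% at about 9 positives and 7.6% at about 7. The team may set it elsewhere, provided it does so before looking at the data.

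The cost is a few lines of text and a software option, with no new data. Intervals become slightly wider, and the test is mildly conservative (about 3-4.5%) at 17 or more positive nodes.
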